4.1.1.6 Definition of Maximum Tolerated Dose

The recommended MTD is the dose with a posterior toxicity probability closest to the target toxicity probability p_T , i.e., closest to 30%. In case all doses have toxicity probabilities greater than $(p_T + \epsilon_2)$, i.e., 35%, no dose will be considered as MTD.

Posterior toxicity probability at each dose level will be estimated based on a beta posterior distribution and application of pooled adjacent violator's algorithm (Yang 2015).

4.1.1.7 Definition of Recommended Phase 2 Dose

The decision regarding the RP2D will take the following into consideration:

- MTD, if reached;
- Pharmacokinetics with or without associated safety and preliminary efficacy findings.

These criteria constitute the basis for RP2D determination. Both the sponsor and the safety review committee (SRC) (Section 4.1.3) must agree on the RP2D.

4.1.2 Dose Expansion Stage (Stage 2)

The safety, tolerability, PK, and preliminary efficacy of HMPL-689 at the MTD/RP2D will be further evaluated in patients with relapsed, refractory, or resistant NHL.

In the dose expansion stage, approximately **CCI** patients will be enrolled in the following cohorts (Table 3), with approximately the indicated number of patients enrolled per cohort.

CCI

Table 3 Number of Planned Patients Enrolled Per Cohort

CCI

^a Patients with prior BTK inhibitor exposure should be either refractory or intolerant to BTK inhibitor therapies listed in [Appendix 16](#).

^b Relapsed, refractory, or intolerant to a BTK inhibitor, where intolerance is defined as treatment discontinuation for ≥ 14 days without disease progression due to ≥ 1 Grade 3 or ≥ 2 Grade 2 non-hematologic toxicities, ≥ 1 Grade 3 neutropenia with infection or fever, or ≥ 1 Grade 4 hematologic toxicity.

The sponsor, in consultation with SRC, may decide to increase or decrease the number of enrolled patients in each cohort depending on preliminary clinical response, safety signals, or operational feasibility. Patients who are not efficacy evaluable in any cohort may be replaced.

Patients will receive oral doses of HMPL-689 QD at the RP2D for continuous 28-day treatment cycles until disease progression, death, intolerable toxicity, at investigator's discretion that the patient can no longer benefit from the study treatment, patient withdrawal from the study, or the end of study, whichever occurs first.

Stopping rules for individual patients in the dose expansion stage are located in [Section 5.8.3.2](#). Stopping rules for dose cohorts or for the study in the dose expansion stage are available in [Section 5.8.4.2](#).

4.1.3 Safety Monitoring

Safety monitoring and dose escalation determination will be conducted by a SRC, which consists of the sponsor's medical monitor, drug safety lead, PK scientists, and the sites' Principal Investigators (PIs) or delegate, as applicable. Safety will be monitored continuously throughout the conduct of this study by the SRC. There will be periodic reviews of emerging data on safety, PK, drug exposure, target engagement, pharmacodynamics, and clinical response to determine continuation (or otherwise) of an individual participant, cohort arm, or entire expansion stage.

The SRC for dose escalation stage may extend to the expansion stage or a new one may replace this SRC, with the same mandate.

4.1.4 Lifestyle Management

Full assessment of extensive non-clinical studies indicated HMPL-689 has no phototoxic effects. Furthermore, experience from ongoing clinical studies in China and Australia also confirm that this study drug lacks any phototoxic effect. Nonetheless, patients enrolled in this study are advised to avoid unnecessary long-term and direct exposure to sunlight or any other source of ultraviolet (UV) light during their participation in the study and until 30 days after the last dose of study drug. Patients are also encouraged to wear sunglasses and apply sunscreen products with protective coefficient of at least SPF 15 whenever possible.

4.1.5 Tumor Assessment and Response Evaluation

Tumor assessment and response evaluation will be performed using the International Workshop on CLL guideline for patients with CLL (Hallek 2008, Cheson 2012), the consensus of International Workshops on WM (IWWM-7 consensus) (Dimopoulos 2014), for patients with LPL/WM, and the Lugano response criteria for patients with other lymphomas (Cheson 2014). Tumor assessment will be conducted every 8 weeks (± 7 days) for the first 24 weeks and every 12 weeks (± 7 days) thereafter. -

Determination of disease progression will occur locally by the investigator in accordance with respective disease criteria.

4.1.6 Safety Follow-Up Period

The safety of all enrolled patients will be closely monitored after the informed consent has been obtained until 30 days post last treatment dose or the initiation of new antineoplastic therapy, whichever comes earlier. After the safety follow-up period, investigators shall only report the follow-up of unresolved SAEs that are related to prior study treatment of HMPL-689. All AEs will be graded in accordance with the National Cancer Institute Common Terminology Criteria for Adverse Events (NCI CTCAE) version 5.0.

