	
Tumor Assessment and Response Evaluation Tumor assessment and response evaluation will be performed using the International Workshop on CLL guideline for patients with CLL, the consensus of International Workshops on WM (IWWM-7 consensus) for patients with LPL/WM, and the Lugano response criteria for patients with other lymphomas. Tumor response will be assessed by investigators according to the response criteria for the respective disease subtypes every 8 weeks (± 7 days) for the first 24 weeks and every 12 weeks (± 7 days) thereafter.
 
Patients who discontinue HMPL-689 treatment due to reasons other than disease progression will continue tumor assessment according to the previous tumor assessment schedule until disease progression, death, end of the study, or start of new antineoplastic therapy, whichever is earlier. Upon implementation of Protocol Amendment 5, this assessment will no longer be required.
 
Determination of disease progression will occur locally by the investigator in accordance with respective disease criteria.
 
Safety Follow-Up Period The safety of all enrolled patients will be closely monitored after informed consent has been obtained until 30 days after the last dose of treatment or the initiation of new antineoplastic therapy, whichever comes earlier. After the safety follow-up period, investigators shall only report the follow-up of unresolved serious adverse events (SAEs) that are related to prior study treatment of HMPL-689.
 
All adverse events (AEs) will be graded in accordance with the National Cancer Institute Common Terminology Criteria for Adverse Events (NCI CTCAE) version 5.0.
 
Extended PFS Follow-Up Period Patients who discontinue HMPL-689 treatment due to reasons other than disease progression will enter the extended PFS follow-up period. During this period, tumor assessment will be conducted quarterly until disease progression, death, the end of the study, or the initiation of new antineoplastic therapy, whichever comes earlier. Upon implementation of Protocol Amendment 5, this assessment will no longer be required.
 
End of Study The end of the study is defined as 18 months after the last patient has been enrolled in the study or all patients have discontinued the study treatment, whichever comes earlier.

Study Treatment
	
HMPL-689 is in capsule formulation for daily oral administration.

CCI
	
CCI

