6.2.5 Adverse Event Reporting Period

After informed consent has been obtained but prior to initiation of study medications, only SAEs will be collected.

After initiation of study medications, all AEs and SAEs regardless of causality will be collected until 30 days after the last administration of study treatment or start of a new treatment of anti-neoplasm therapy, whichever is earlier. After this period, investigators should report only SAEs that are related to prior study treatment of HMPL-689 (see Section 6.7).

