6.7 Post Study Adverse Events

At the last scheduled visit, the investigator should instruct each patient to report to the investigator any subsequent SAEs that the patient's personal physician believes could be related to prior study treatment.

The investigator should notify sponsor or sponsor's designee of any death or other SAE occurring at any time after a patient has discontinued or terminated study participation if related to prior study treatment. The investigator is not obligated to actively monitor patients for AEs once the trial has ended. Sponsor or sponsor's designee should also be notified if the investigator should become aware of the development of cancer or of a congenital anomaly in a subsequently conceived offspring of a patient that participated in this study.

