17.2. ADVERSE EVENTS

Treatment-emergent adverse events (TEAEs) are defined as AEs with onset date on or after the first dose of study medication and no later than 30 days after the date of last study treatment administration or start of a new treatment of anti-neoplasm therapy, whichever is earlier. An exception is that study medication related SAE collected later than 30 days after the last treatment date or start of a new treatment of anti-neoplasm therapy will be treated as TEAEs.

Refer to Section 7.10 for handling of partial dates for AEs. In the case where it is not possible to classify an AE as treatment-emergent or not, the AE will be classified as treatment-emergent.

All AEs will be listed, and only TEAE will be summarized.

The missing severity will be classified as grade 3. Relationship, as indicated by the Investigator, is classified as "Not related", "Related". TEAEs with a missing relationship to study medication will be regarded as "related" to study medication.

Protocol Number: 2018-689-00US1 Page 37 of 43

TEAE OVERVIEW

An overall summary of TEAEs will include the number of patients with:

- Any TEAE
- Any TEAEs by maximum CTCAE grade
- Any TEAE of CTCAE Grade 3 or higher
- Any TEAE Leading to Dose Modification
 - Any TEAE Leading to Dose Reduction
 - o Any TEAE Leading to Drug Interruption
- Any TEAE Leading to Drug Discontinuation
- Any TEAE Leading to Death
- Any Treatment Related TEAE
- Any Treatment Related TEAE of CTCAE Grade 3 or higher
- Any Treatment Related TEAE Leading to Dose Modification
 - Any Treatment Related TEAE Leading to Dose Reduction
 - Any Treatment Related TEAE Leading to Drug Interruption
- Any Treatment Related TEAE Leading to Drug Discontinuation
- Any Treatment Related TEAE Leading to Death
- Any Serious TEAE
- Any Treatment Related Serious TEAE
- Any Special Interest TEAE (AESI)
- Any Treatment Related AESI

TEAE SUMMARY

All TEAE will be summarized (the number and percent of patients) by SOC, PT and maximum CTCAE grade (All Grade, Grade ≥3, Grade 1/2).

The following categories will be summarized (the number and percent of patients) by PT and maximum CTCAE grade (All Grade, Grade ≥3, Grade 1/2).

	Summary scope
	- Any TEAE
	- TEAEs with CTCAE grade 3 or higher (maximum CTCAE
	grade by Grade 5, Grade 4, Grade 3)
TEAE	- TEAEs leading to dose modification
TEAE	 TEAEs leading to dose interruption
	 TEAEs leading to dose reduction
	- TEAEs leading to discontinuation of study drug

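### After the safety follow-up window, the synopsis and protocol 4.1.6 leave out new drug-related SAEs that 6.2.5 and 6.7 require and SAP 17.2 would count as TEAEs

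*Protocol*

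**What the plan says.** Four places in the protocol and one in the SAP deal with SAEs after the safety follow-up period.

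- **Protocol 4.1.6 (Safety Follow-Up Period):** after the period, "investigators shall only report the follow-up of unresolved SAEs that are related to prior study treatment of HMPL-689".
- **Protocol synopsis, same topic:** "investigators shall only report the follow-up of unresolved serious adverse events (SAEs) that are related to prior study treatment of HMPL-689".
- **Protocol 6.2.5 (Adverse Event Reporting Period):** all AEs and SAEs are collected "until 30 days after the last administration of study treatment or start of a new treatment of anti-neoplasm therapy, whichever is earlier". It continues: "After this period, investigators should report only SAEs that are related to prior study treatment of HMPL-689", and it refers the reader to 6.7.
- **Protocol 6.7 (Post Study Adverse Events):** the investigator is to notify the sponsor of "any death or other SAE occurring at any time after a patient has discontinued or terminated study participation", on condition that the event is related to prior study treatment. At the last visit, patients are told to report later SAEs that their own physician thinks could be related.
- **SAP 17.2:** TEAEs normally stop at the same boundary, but a "study medication related SAE collected later than 30 days after the last treatment date", or after the start of new antineoplastic therapy, is also treated as a TEAE.

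**The concern.** The sentence in the synopsis and 4.1.6 is exclusive: it names one thing that may still be reported, namely follow-up on related SAEs that are already open. A related SAE with first onset after the window is not an open event. Under that sentence it goes unreported; under 6.2.5 and 6.7 it must be reported. A site cannot follow both.

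What is at stake is complete capture of serious late toxicity, and with it part of the primary safety endpoint. The Stage 1 endpoints name SAEs and treatment-related SAEs. The Stage 2 endpoint is safety, including TEAEs and treatment-related AEs. Because the SAP extends the TEAE definition to late related SAEs, an omitted event could drop out of the TEAE, serious TEAE and treatment-related TEAE tables. Any error would be towards lower counts.

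The rule is still in use. Under Amendment 5, enrolled patients who are benefiting may stay on treatment, so their post-treatment windows are yet to come.

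**Working it through.** No sample size, power or event count is involved, and the plan states no figure to reproduce. The check sets the rules side by side.

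**Step 1: is the window the same?** Yes. 4.1.6, the synopsis and 6.2.5 all end it at the earlier of 30 days after the last dose and the start of new antineoplastic therapy. The difference lies in what is reported afterwards, not in when the period ends.

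**Step 2: apply each rule to the possible cases.**

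| Drug-related SAE | Synopsis and 4.1.6 | 6.2.5 and 6.7 | SAP 17.2 |
|---|---|---|---|
| Starts inside the window, unresolved at its close | Follow-up reported | Reported | TEAE |
| First onset more than 30 days after last dose | Not reported, read literally | Reported | TEAE if collected |
| First onset within 30 days of last dose, but after new antineoplastic therapy has started | Not reported, read literally | Reported | TEAE if collected |

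The first row agrees throughout; the other two conflict. The third row shows that the gap can open before Day 30.

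**Step 3: which scope do the documents otherwise support?** 6.2.5 sets no limit to unresolved events and points to 6.7. 6.7 speaks of related events occurring at any time and of subsequent ones. SAP 17.2 makes room for them. These three fit together; the sentence in the synopsis and 4.1.6 is the odd one out.

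**Step 4: what would an omitted event do to the tables?** SAP 17.2 reports numbers and percentages of patients and counts a patient once per SOC or PT, at the worst grade. For a line with *n* patients out of *N*:

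- if the omitted event was the patient's only qualifying event on that line, the reported result is (*n* − 1)/*N* instead of *n*/*N*;
- if the patient already has a qualifying event on that line, the result stays *n*/*N*, although the grade shown may change.

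The effect can therefore differ from line to line for the same patient. *N* differs too: SAP Section 8 presents safety by dose level and total in Stage 1, and by malignancy type and total in Stage 2. No document gives a rate of late-onset related SAEs, so the calculation cannot go further.

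**Step 5: is there another route by which late events would surface?** Amendment 5 narrows it. Protocol 4.1.7 no longer requires the quarterly extended PFS assessments, and 5.7.13 and 5.8.2 say that patients who stop treatment for reasons other than progression also leave the study. Late capture then rests largely on what sites choose to send, which makes the written rule matter more.

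**The case against.** The strongest reply is that 4.1.6 is a short summary in the design section and that the operative rules sit in Section 6. Protocol 6.2.5 and 6.7 state the broader duty, and 6.4.1 asks for all SAEs within 24 hours of the investigator learning of them, whatever the attribution, with no post-treatment cut-off stated there. An event would be lost only at a site that relied on the summary and overlooked all of these. This stands as a limit on likelihood: late related SAEs could be missed, but the documents do not show that any have been or will be.

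A second reply is that 4.1.6 can be read as limiting which open events still need follow-up reports, without barring first reports of new ones. That reading is possible, but the sentence says that only such follow-up is to be reported, and nothing in 4.1.6 or the synopsis refers the reader to the wider rule.

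Third, 6.7 does not oblige investigators to monitor actively once the trial has ended, so late capture is partly passive even under the broader rule. Harmonising the text would not make capture complete.

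A reader might also infer that the SAP requires these events to be collected. It does not; it only says how to classify those that are.

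**Conclusion.** The point holds as an internal inconsistency in current protocol text. One stated rule excludes new-onset related SAEs after the window; another requires them. Sites that follow the synopsis or 4.1.6 could omit such events, so capture may be uneven and counts of serious and treatment-related TEAEs could be understated. This rests on a literal reading of the restrictive sentence and on at least one site acting on it.

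The size cannot be determined from the documents. Three stronger readings are tempting and unsupported:

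- **That each missed event costs a fixed amount, for example one patient in the roughly 100 expected in Stage 2.** The tables count patients once per line, so an omission may change nothing, and the denominators for individual malignancy types are smaller than the total.
- **That the missing events would mostly be Grade 3 or higher.** Nothing in the documents says so, and protocol 6.2.2 has severity and seriousness assessed independently.
- **That the primary safety tables as a whole depend on which section a site followed.** Only related SAEs with onset after the window are affected, and only at sites that follow the narrower sentence.

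It should be corrected because the affected events are serious and drug-related, they bear on the primary safety endpoint, and the correction is small.

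**What to change.** Reconcile the sentence in the synopsis and in 4.1.6 with the reporting scope of 6.2.5 and 6.7: after the safety follow-up period, investigators report any SAE considered related to HMPL-689, whether newly occurring or unresolved. A cross-reference from 4.1.6 to 6.2.5 and 6.7 would keep the places aligned. SAP 17.2 needs no change for this point.

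Before database lock, query sites once for related SAEs with onset after the window, naming both ways in which it can close, so that events already left out can still enter the final analysis.

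The cost is one sentence in two places and one round of site queries. It adds no duty beyond what 6.2.5 and 6.7 already impose.

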4.1.7 Extended Progression-Free Survival Follow-Up Period

Patients who discontinue HMPL-689 treatment due to reasons other than disease progression will enter the extended PFS follow-up period. During this period, tumor assessment will be conducted quarterly until disease progression, death, the end of the study or the initiation of new anti-neoplastic therapy, whichever is earlier.

Upon implementation of Protocol Amendment 5, this assessment will no longer be required.

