5.7.13 Tumor and Response Evaluation

The baseline tumor assessment can be completed within 21 days prior to the first dose of IP (depending on the patient's disease status a window may be acceptable based on a discussion between the investigator and the sponsor's medical monitor). All measurable and evaluable lesions should be assessed and documented at screening and each subsequent tumor evaluation, using blood test, physical examination, contrast enhanced CT scans (neck, chest, abdomen, and pelvis) for non-fluorodeoxyglucose (FDG)-avid lymphomas (e.g., LPL/WM, CLL/SLL, and MZL) and/or positron emission tomography(PET)-CT scans for patients with FDG-avid lymphomas

(e.g., FL, MCL, and DLBCL). Enhanced magnetic resonance imaging (MRI) may be used instead of CT scans in patients for whom CT scans are contraindicated.

Tumor assessment will be conducted every 8 weeks (± 7 days) for the first 24 weeks and every 12 weeks (± 7 days) thereafter. Patients who discontinue HMPL-689 treatment due to reasons other than disease progression will continue tumor assessment according to previous tumor assessment schedule till disease progression, death, end of the study, or start of a new anti-neoplastic therapy, whichever is earlier (see [Appendix 1](#)). Upon implementation of Protocol Amendment 5, patients who discontinue HMPL-689 treatment due to reasons other than disease progression will also discontinue from the study.

The same imaging procedure and laboratory tests used to define measurable lesions at baseline should be used throughout the study for each patient.

Bone Marrow Aspirate and Biopsy

A bone marrow biopsy or aspirate is strongly recommended to be done at baseline or up to 3 months before of the Cycle 1 Day 1 and for confirmatory purposes for all patients who achieved a radiologic CR or to confirm suspected progressive disease (PD) based solely upon declines in the platelet count and/or hemoglobin. Upon implementation of Protocol Amendment 5, this assessment will no longer be required.

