5.8.2 Extended Progression Free Survival Follow-up

Patients who discontinue HMPL-689 treatment due to reasons other than disease progression will enter the extended PFS follow-up period. During this period, tumor assessment will be conducted quarterly until disease progression, death, the end of the study or the initiation of new antineoplastic therapy, whichever comes earlier. The assessments to be performed at the follow-up visits are listed in [Appendix 1](#). Upon implementation of Protocol Amendment 5, patients who discontinue HMPL-689 treatment due to reasons other than disease progression will also discontinue from the study.

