7	No post-baseline tumor	Date of first dose	Censored	No post-baseline
	No post-baseline tumor evaluable assessment and alive			assessment
7 8	No post-baseline tumor evaluable assessment and alive New anti-cancer treatment	Date of last evaluable	Censored	assessment Initiation of new anti-
	No post-baseline tumor evaluable assessment and alive			assessment

		treatment or date of first dose (if no post- baseline tumor assessment before new anti-cancer)		
9	No disease progression or death Note: use last tumor assessment before two or more consecutive missed/non-evaluable tumor assessments (if exists)	Date of last evaluable	Censored	Progression free at time of analysis: the patient is known to be alive without any progression happened at the data cut- off date

Note: Only for tumor assessments and death date before cutoff date.

[a] time period that identifies two consecutive missed/non-evaluable tumor assessments is calculated as 2*(the planned duration between assessments + protocol allowed visit window) from the last evaluable tumor assessment or (2*the planned duration between assessments + 1*protocol allowed visit window) from date of first dose (if no post-baseline evaluable tumor assessment).

According to protocol, tumor assessment will be conducted every 8 weeks for the first 24 weeks and every 12 weeks thereafter (±7 days). Given the schedules visit assessment scheme, the definition of two missed consecutive tumor assessment visit may vary, please refer to following rule:

- If the last evaluable tumor assessment before PD/death is on or before Day 105 (week 15, which is 8 weeks before week 24, and allowing for 7 days for early visit, hence 7*16 weeks 7 days for a late visit =Day 105), then two consecutive assessments equates to 126 days since last evaluable tumor assessment, allowing for early and late visits (2*8 weeks + 7 days for an early assessment + 7 days for a late assessment), or 119 days since date of first dose, allowing for late visit (2*8 weeks + 7 days for a late assessment).
- If the two missed assessments occur over the period when the scheduled frequency of tumor assessments change from 8-weekly to 12-weekly, which means last evaluable tumor assessment is from week 16 to 23 (Day 106 to Day 161), then two consecutive assessments equates to 154 days (7*8 weeks + 7*12 weeks + 7 days for an early assessment + 7 days for a late assessment) since last evaluable tumor assessment.

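### The SAP's 126- and 154-day PFS limits count one missed quarterly off-treatment scan as two, and the protocol contradicts itself on whether that schedule applied before Amendment 5

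*Protocol*

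**What the plan says.** **Off-treatment scans.** The protocol gives two schedules for patients who stop for reasons other than progression.

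- Quarterly: section 4.1.7, "tumor assessment will be conducted quarterly until disease progression, death, the end of the study or the initiation of new anti-neoplastic therapy", and section 5.8.2, "During this period, tumor assessment will be conducted quarterly until disease progression, death, the end of the study".
- Previous schedule: section 5.7.13, "will continue tumor assessment according to previous tumor assessment schedule till disease progression, death, end of the study".
- Both: the synopsis has "will continue tumor assessment according to the previous tumor assessment schedule until disease progression" under tumor assessment, and quarterly scans under extended PFS follow-up.

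The previous schedule is "every 8 weeks (± 7 days) for the first 24 weeks and every 12 weeks (± 7 days) thereafter" (4.1.5). Each passage adds that, once Amendment 5 is implemented, these scans are no longer required or the patient leaves the study.

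**Censoring.** SAP 16.5, Table 2, rows 2 and 4, censor a death or progression that comes after two or more consecutive missed or non-evaluable scans. The censoring date is the last evaluable scan, or first dose if there is none. Footnote [a] says the qualifying period is "calculated as 2*(the planned duration between assessments + protocol allowed visit window) from the last evaluable tumor assessment". It then fixes the limits by the day of the last evaluable scan:

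- by Day 105, "two consecutive assessments equates to 126 days since last evaluable tumor assessment";
- Day 106 to 161, 154 days;
- from Day 162, 182 days;
- with no post-baseline scan, 119 days from first dose.

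No limit is given for quarterly follow-up.

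**The concern.** The general rule depends on the planned interval between scans, but the fixed limits do not: they look only at when the last evaluable scan took place. A patient who stopped early, for toxicity say, and moved to quarterly scans has a longer planned interval than the limits assume. One missed scan can then look like two, and a progression or death that the rule means to count becomes a censored time at the previous scan. At stake are the PFS curve and its 6- and 12-month rates. PFS is analysed in the FAS, so patients followed off treatment before Amendment 5 stay in the analysis.

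**Working it through.** **Inputs.** On-treatment interval 56 days to week 24, then 84 days, with a window of 7 days either way (Protocol 4.1.5). The formula and limits come from SAP 16.5. The text does not give quarterly in days, so I take a quarter q of 84 to 91 days as an assumption, and assume the same 7-day window.

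**Reproducing the SAP's limits.**

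- 2 × (56 + 7) = 126
- 56 + 84 + 7 + 7 = 154
- 2 × (84 + 7) = 182
- 2 × 56 + 7 = 119 from first dose

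All agree. On the 8/12-week schedule, exactly one missed scan leaves a gap of 112, 140 or 168 days, give or take 14, so at most 126, 154 or 182 days. Each limit is the longest gap that one missed scan can produce, and the rule works as intended there.

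**The gap on quarterly scans.** With exactly one missed scan, counting from the last evaluable scan, the gap is 2q, give or take 14 days because both visits have a window:

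- q = 84: 168 days (154 to 182)
- q = 91: 182 days (168 to 196)

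| Last evaluable scan | SAP limit | q = 84 | q = 91 |
|---|---|---|---|
| By Day 105 | 126 | always exceeded (nominal excess 168 − 126 = 42) | always exceeded (182 − 126 = 56) |
| Day 106 to 161 | 154 | exceeded unless the gap is exactly 154 (168 − 154 = 14) | always exceeded (182 − 154 = 28) |
| From Day 162 | 182 | never exceeded (maximum 182) | nominal gap equals the limit; exceeded only at 183 to 196 days |

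In the first two rows, progression found at the scan after a single missed one is censored under row 4. Deaths behave likewise under row 2. With q = 91, a death 127 to 182 days (limit 126) or 155 to 182 days (limit 154) after the last scan is censored although only the scan due at 91 days was missed.

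**What the SAP's own formula gives.** From the last evaluable scan: 2 × (84 + 7) = 182 or 2 × (91 + 7) = 196 days. From first dose: 2 × 84 + 7 = 175 or 2 × 91 + 7 = 189 days, against the fixed 119.

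**The transition.** If the quarter runs from the last scan and none is missed, the gap is at most q + 14 = 98 or 105 days, and no limit is exceeded. If it runs from the end of treatment, a patient last scanned on Day 57 passes 126 days with no quarterly scan missed, once treatment stops more than 126 − 91 = 35 days (or 126 − 84 = 42 days) after that scan.

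**The case against.** The case on the other side is substantial.

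- **The general rule is already right.** Footnote [a] is written in terms of the planned interval and says the definition may vary. That is true, but the fixed limits are what would be programmed, and they contradict the rule for anyone on quarterly scans.
- **Amendment 5 ended these scans.** Enrolment has stopped and reconciling the protocol changes no future scan. This stands: only earlier follow-up is affected. Those data nevertheless remain in the final PFS analysis.
- **The interval is not established.** Protocol 5.7.13 and 5.8.2 refer to Appendix 1, which is not in the text available here and may define it. This also stands, so the result is given as a range.
- **Many conditions must coincide.** The patient must have stopped without progression, been on the quarterly version, been last scanned by Day 161, missed a scan (or fallen in the transition gap), and then progressed or died without new therapy, since rows 5 and 8 censor after new therapy anyway. PFS is a secondary, descriptive endpoint in a phase 1 study, and censoring reasons are tabulated and listed by patient. This limits importance, not correctness.
- **The direction is not guaranteed.** Row 9 also cuts event-free patients back to the scan before such a gap, which offsets part of the effect. An upward shift remains the expected direction, because true events are removed and patients who are doing badly are more likely to miss scans.

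A reader might infer that DoR is biased in the same way. SAP 16.6 counts progression or death from any cause as the event and invokes the PFS censoring rules for patients who have neither. Read literally, rows 2 and 4 then remove no DoR event, and the text does not settle whether that reading is meant.

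**Conclusion.** The point holds, within limits. The protocol passages contradict each other. For patients actually followed quarterly before Amendment 5 and last scanned by Day 161, the 126-day limit always treats one missed scan as two, and the 154-day limit does so except at its extreme on an 84-day quarter. PFS events are then censored that the SAP's own formula would count.

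Three stronger readings go too far:

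- That every missed quarterly scan is double-counted. From Day 162 the 182-day limit covers one missed scan on a 12-week quarter and is borderline on a 13-week quarter.
- That 196 days is the correct limit. It rests on a 91-day quarter; at 84 days the formula returns 182, already the SAP's figure from Day 162.
- That events are known to have been lost. The documents give no count of patients on quarterly follow-up or of missed scans, so the size of any bias cannot be computed.

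This is a minor correction to the analysis rule.

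**What to change.** 1. Reconcile Protocol 4.1.7, 5.8.2, 5.7.13 and the synopsis by stating which off-treatment schedule applied before Amendment 5. Define quarterly in days, and say whether it runs from the last scan or from the end of treatment.
2. In SAP footnote [a], apply the stated formula from the last evaluable scan with the interval in force for each patient: 182 days for an 84-day quarter, 196 for a 91-day quarter. Cover the step from the last on-treatment scan to the first quarterly scan, and the limit from first dose (175 or 189 days).
3. Instead or in addition, run a PFS sensitivity analysis that counts every progression and death as an event regardless of missed scans.
4. Say in SAP 16.6 whether rows 2 and 4 apply to DoR.

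The cost is a sentence or two in the SAP, a flag for off-treatment follow-up and a little more programming. No further data collection is needed beyond the existing scan and discontinuation dates.
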